11.7.2. Elevated Liver Function Tests

Before a monthly dose of DAC HYP is given, LFT results from a prior test (performed within the previous 32 days) must be reviewed by the *Study Neurologist* or their backup, and must be within the protocol-required limits shown below (LFT procedures are described in Section 14.4.3).

If a subject develops clinical signs or symptoms suggestive of hepatic dysfunction (e.g., unexplained nausea, vomiting, abdominal pain, fatigue, anorexia, or jaundice and/or dark

CONFIDENTIAL

The information contained herein may not be used, disclosed, or published without the written consent of Biogen MA Inc.

urine), promptly measure serum transaminases and interrupt or discontinue treatment with DAC HYP, as appropriate.

Table 8 summarizes how subjects with elevated LFTs will be managed during the study.

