11.7.2.3. Second Temporary Suspension Due to Elevated LFTs

If a subject has treatment suspended for an LFT elevation and has also had a prior treatment suspension for an LFT elevation during DAC HYP use, DAC HYP must be permanently

CONFIDENTIAL

The information contained herein may not be used, disclosed, or published without the written consent of Biogen MA Inc.

discontinued unless an alternative explanation for the LFT elevation unrelated to DAC HYP use is clearly identified by the Investigator.

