11.7.2.4. Management Guidelines Following Temporary Suspension or Permanent Discontinuation

All subjects with elevated LFTs (**ALT/SGPT or AST/SGOT >3×ULN**) should be managed per the guidelines below.

- Study treatment must be temporarily suspended and LFT elevation should be confirmed as soon as possible but no later than 1 week by a repeat test performed at the central laboratory. In cases where LFTs cannot be performed via the central laboratory, repeat LFT results from a local laboratory can be used for confirmation.
- After a temporary suspension, dosing of DAC HYP may be resumed when ALT/SGPT and AST/SGOT are <2×ULN provided that the criteria for permanent discontinuation have not been met (see Section 11.8).
- For subjects that have had DAC HYP treatment suspended for >8 weeks due to elevated LFTs, Investigators should consider whether subjects should permanently discontinue treatment with DAC HYP in order to allow treatment with another disease-modifying therapy and minimize the risk of return of MS disease activity. Such decisions are at the discretion of the Investigators and their assessment of risks and benefits.
- All subsequent testing after a temporary treatment suspension or permanent discontinuation is required to be performed centrally *at least weekly* until the LFT elevation is <2×ULN.
- Monitoring of LFT elevations will occur for up to 6 months after the last DAC HYP dose has been administered. If after 6 months the LFT remains elevated at ≥2×ULN, the Investigator or health care professional should continue to monitor the LFT as clinically appropriate; any relevant follow-up data should be reported to the Sponsor as a spontaneous report.
- A careful review of all concomitant medications must be documented. The Investigator should consider discontinuation of all potential hepatotoxic medications. All recently started or non-essential concomitant medications should be suspended until the LFT elevation is <2×ULN.
- An Unscheduled Hepatic Assessment Visit as soon as possible but within 1 week should be performed in the event of permanent discontinuation due to elevated LFTs (see Table 6).

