- Subjects should be referred to a hepatic specialist if medically indicated. In consultation with the hepatic specialist, a full evaluation of alternative causes of liver injury should be performed. Additional hepatic studies should be performed according to local standard of care. The central laboratory may be utilized for additional hepatic testing per Investigator request. If testing for viral hepatitis is negative, LFT elevations are not improving, DAC HYP is suspected as the cause of

CONFIDENTIAL

The information contained herein may not be used, disclosed, or published without the written consent of Biogen MA Inc.

the LFT elevation, and there are no known contraindications for corticosteroids, then, in continued consultation with the hepatic specialist, empiric treatment with systemic corticosteroids should be considered.

Table 8: Summary of Management of Subjects With Elevated Liver Function Tests

Total Bilirubin	Serum Transaminases		
	ALT/SGPT or AST/SGOT >3 to ≤5×ULN	ALT/SGPT or AST/SGOT >5×ULN	Second Temporary Suspension Due to Elevated ALT/SGPT or AST/SGOT
≤2×ULN	Temporarily suspend dosing ¹ Weekly LFT until both ALT/SGPT and AST/SGOT are <2×ULN	Withhold dosing ² Repeat test as soon as possible but no later than 1 week after the elevation If confirmed, permanently discontinue study treatment. Otherwise, follow the guidelines in Section 11.7.2.4.	Withhold dosing ² Repeat test as soon as possible but no later than 1 week after the elevation If confirmed, permanently discontinue study treatment. Otherwise, follow the guidelines in Section 11.7.2.4.
>2×ULN	Withhold dosing ² Repeat test as soon as possible but no later than 1 week after the elevation If confirmed, permanently discontinue study treatment. Otherwise, follow the guidelines in Section 11.7.2.4.	As above	As above

ALT = alanine aminotransferase; AST = aspartate aminotransferase; LFT = liver function test; SGOT = serum glutamic oxaloacetic transaminase; SGPT = serum glutamic pyruvic transaminase; ULN = upper limit of normal.

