¹ Subjects should be managed according to the following guidelines: LFT elevation should be confirmed as soon as possible but no later than 1 week; LFT is required to be performed *at least weekly* until the LFT elevation is <2×ULN; dosing of DAC HYP may be resumed when ALT/SGPT, AST/SGOT, and bilirubin are <2×ULN, provided that the criteria for permanent discontinuation have not been met; a careful review of all concomitant medications must be documented; and if treatment is permanently discontinued, subjects should be referred to a hepatic specialist if medically indicated.

² Subjects should be managed according to the following guidelines: LFT elevation should be confirmed as soon as possible but no later than 1 week; LFT is required to be performed *at least weekly* until the LFT elevation is <2×ULN; an Unscheduled Hepatic Assessment Visit is performed as soon as possible but within 1 week of the elevation; a careful review of all concomitant medications must be documented; and if treatment is permanently discontinued, subjects should be referred to a hepatic specialist if medically indicated.

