11.8. Discontinuation of Study Treatment

A subject *must* permanently discontinue DAC HYP for any of the following reasons:

- The subject becomes pregnant. Study treatment must be discontinued immediately. Report the pregnancy according to the instructions in Section 15.5.4.
- The subject experiences a hypersensitivity or suspected allergic reaction (e.g., anaphylaxis and anaphylactoid reactions) to study treatment.
- The subject develops a chronic viral infection (e.g., hepatitis C, HIV).
- The subject develops elevated LFTs that meet any of the following criteria:
 - ALT/SGPT or AST/SGOT $>5\times$ ULN that is confirmed by a repeat test performed within 1 week
 - ALT/SGPT or AST/SGOT $>3\times$ ULN with concomitant elevation of total bilirubin $>2\times$ ULN that is confirmed by a repeat test performed within 1 week
 - If a subject has treatment suspended for an LFT elevation and has also had a prior treatment suspension for an LFT elevation during DAC HYP use, DAC HYP must be permanently discontinued unless an alternative explanation for the LFT elevation unrelated to DAC HYP use is clearly identified by the Investigator.
- The subject experiences a cutaneous AE, which the Investigator (in consultation with the *Study Dermatologist*) considers to be a generalized allergic or hypersensitivity reaction to study treatment (see Section 11.7.3).
- The subject experiences inflammatory colitis, except in subjects with mild colitis who require DAC HYP therapy and have a positive benefit-risk profile per Investigator's assessment and the subject's informed decision (see Section 11.7.4).
- The subject requires treatment with any of the disallowed concomitant medications, unless approval is given by the Biogen Medical Director(s) or Advisory Committee. Note: IVMP for treatment of a protocol-defined relapse is allowed as detailed in the protocol (see Section 11.5). Treatment with valproic acid, carbamazepine, lamotrigine, or phenytoin is only allowed under the conditions detailed in the protocol.
- The subject experiences a medical emergency that necessitates permanent discontinuation of treatment.
- The subject desires to discontinue treatment under this protocol.
- At the discretion of the Investigator for medical reasons or for non-compliance.
- Upon confirmatory tests 1 month apart, the subject's hematology results are as follows in the absence of an identified reversible cause by the Investigator (e.g., infection):

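### Table 8 conflicts with the hepatic text on stopping after a second suspension and on the hepatic visit, and differs narrowly on bilirubin for resuming; each time the table is stricter

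*Protocol*

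**What the plan says.** Section 11.7.2 states that Table 8 "summarizes how subjects with elevated LFTs will be managed during the study". The differences all lie within the current protocol text.

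- **Second suspension.** In the column headed "Second Temporary Suspension Due to Elevated ALT/SGPT or AST/SGOT", the bilirubin ≤2×ULN cell of Table 8 withholds dosing, asks for a repeat test within 1 week and continues: "If confirmed, permanently discontinue study treatment. Otherwise, follow the guidelines in Section 11.7.2.4". The cell below it, for bilirubin >2×ULN, refers back to it. Section 11.7.2.3 instead requires DAC HYP to be permanently "discontinued unless an alternative explanation for the LFT elevation unrelated to DAC HYP use is clearly identified by the Investigator". The mandatory list in Section 11.8 repeats this: "permanently discontinued unless an alternative explanation for the LFT elevation unrelated to DAC HYP use is clearly identified by the Investigator". Neither section makes this rule depend on a repeat test. The other two LFT criteria in Section 11.8 do require confirmation (ALT/AST >5×ULN, or >3× "ULN with concomitant elevation of total bilirubin" >2×ULN), and they have no alternative-cause exemption.
- **Hepatic visit.** Footnote 2 to Table 8 applies wherever dosing is withheld and sets the visit within 1 week of the elevation. Section 11.7.2.4 asks for it in the event of permanent discontinuation and points to Table 6. Table 6 (footnote 1) and Sections 14.1 and 14.8 count the week from discontinuation due to elevated LFTs. Section 13.2 requires the comprehensive hepatic panel only in subjects who permanently discontinue for that reason.
- **Resumption.** Footnote 1 says that "dosing of DAC HYP may be resumed when ALT/SGPT, AST/SGOT, and bilirubin are" <2×ULN. Sections 11.7.2.1 and 11.7.2.4 name only ALT and AST, and allow resumption "provided that the criteria for permanent discontinuation have not been met (see Section 11.8").

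**The concern.** Section 5.1 reports an increased incidence of transaminase elevations and serious hepatic events in Study 205MS301, so these are working rules that sites will need. A table of this kind is likely to be what staff consult when a result arrives. If it disagrees with the text, two sites that both follow the protocol could make opposite decisions for the same subject, one stopping permanently and the other re-dosing. They could also differ on whether a subject who stays on treatment has a hepatic visit and panel, and by when.

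**Working it through.** The protocol gives no figure to reproduce. The check sets the rules side by side over every combination of the factors they use.

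**Inputs** (Table 8; Sections 11.7.2.1 to 11.7.2.4 and 11.8): ALT/AST >3 to ≤5 or >5×ULN; bilirubin ≤2 or >2×ULN; repeat test confirms or not; and, for a second episode, other cause clearly identified or not.

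First episode: 2 × 2 × 2 = 8. Second episode: 8 × 2 = 16. Total 24.

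**Step 1: stop decision.**

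- Text: stop if confirmed and (ALT/AST >5×ULN or bilirubin >2×ULN), or if it is a second episode with no other cause.
- Table 8: stop if confirmed, except for a first episode >3 to ≤5×ULN with bilirubin ≤2×ULN, which is only suspended. Unconfirmed cases go to Section 11.7.2.4, which defers to Section 11.8.

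| Group | Number | Result |
|---|---|---|
| First episode | 8 | Agree (3 stop, 5 do not) |
| Second, no other cause, confirmed | 4 | Agree: stop |
| Second, no other cause, unconfirmed | 4 | Text stops; the table cell does not say so, but 11.7.2.4 leads to 11.8, which does |
| Second, other cause, confirmed | 4 | 3 agree: stop; 1 direct conflict |
| Second, other cause, unconfirmed | 4 | Agree: no mandatory stop |

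Agree: 8 + 4 + 3 + 4 = 19. Resolved only by cross-reference: 4. Direct conflict: 1 (>3 to ≤5×ULN, bilirubin ≤2×ULN, confirmed, other cause). 19 + 4 + 1 = 24.

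**Step 2: who has the hepatic visit.** Footnote 2 covers every combination except the two first-episode ones at >3 to ≤5×ULN with bilirubin ≤2×ULN: 24 − 2 = 22. The text asks for a visit where it stops treatment: 3 first-episode + 11 second-episode (8 without and 3 with another cause) = 14, all within the 22. Footnote 2 alone asks for it in 22 − 14 = 8: 3 first-episode unconfirmed, 4 second-episode unconfirmed with another cause, and the 1 direct conflict. Neither asks in 2.

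**Step 3: latest visit date.** Count the elevation as day 0 and let the repeat result come on day r, with r ≤ 7. Footnote 2 gives day 7. Where the stop waits for confirmation, the text gives day r + 7: day 9 if r = 2, and up to about day 14 if r = 7. This applies to 3 first-episode + 3 second-episode (other cause identified) = 6 of the 14. In the other 8 (second episode, no other cause) the text's stop does not depend on the repeat test, and no time limit is given for seeking another cause, so day 14 does not follow there.

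**Step 4: resumption.** Footnote 1 is attached only to the cell with bilirubin ≤2×ULN. The criteria differ only if bilirubin is exactly 2×ULN, or has risen to ≥2×ULN by the time ALT and AST are <2×ULN. Example: ALT 4×ULN and bilirubin 1.5×ULN at suspension; later ALT and AST 1.5×ULN and bilirubin 2.5×ULN. Footnote 1 bars resumption. The criterion in Sections 11.7.2.1 and 11.7.2.4 is met, and the bilirubin criterion in Section 11.8 is not, because ALT/AST is no longer >3×ULN.

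**The case against.** The strongest reply is that Table 8 is titled a summary and that Section 11.8 holds the mandatory list. The column header repeats the heading of Section 11.7.2.3, where the full rule stands, so a careful reader would follow the text. Only 1 combination in 24 conflicts directly on stopping, and there the table errs toward stopping, which Section 11.8 already leaves open to the Investigator for medical reasons. On resumption, Section 11.7.2.1 requires suspension for any other hepatic condition that the Investigator finds clinically significant, including jaundice, and resuming is optional in any case.

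Much of this stands. In every real difference Table 8 is the stricter source: it stops one more type of subject, asks for the visit earlier and more widely, and adds bilirubin before re-dosing. The resumption point is narrow. What does not stand is that the summary label settles the matter. No section says which source governs, and the missing exemption leads to a permanent stop.

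A reader might infer that Table 8 is the less safe rule, because it makes a second-suspension stop depend on confirmation. The documents do not support that: the unconfirmed branch goes to Section 11.7.2.4 and from there to Section 11.8, which requires the stop. A reader might also infer that the primary endpoint is compromised. It is not: Sections 15.2.2 and 15.6 require all AEs to be recorded whatever their severity or relationship to treatment.

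**Conclusion.** The protocol contradicts itself in two places and differs narrowly in a third, and this should be corrected. On stopping, there is one direct conflict, plus four combinations in which the table's silence is repaired only by following two cross-references. On the hepatic visit, footnote 2 alone asks for it in eight combinations, all in subjects who need not stop under the text. The deadline can differ by up to about a week where the stop waits for a repeat test. On resumption, the criteria part only when bilirubin is at or above 2×ULN after suspension. First-episode stopping rules agree throughout.

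The consequence is inconsistent management: permanent stops that the text does not require, and visits and panels done at some sites and not at others. The counts assume that each factor splits as the protocol words it and that the repeat result is known on the day of the test. The documents give no rates for these combinations, so no number of affected subjects can be stated.

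**What to change.** - **Second suspension.** In that column of Table 8, write the rule of Sections 11.7.2.3 and 11.8: stop permanently unless a cause unrelated to DAC HYP is clearly identified and no other LFT criterion in Section 11.8 is met. State in Table 8, Section 11.7.2.3 and Section 11.8 alike whether confirmation is required; the sponsor has to decide this.
- **Hepatic visit.** Align the trigger and clock in footnote 2 with Sections 11.7.2.4, 13.2, 14.1 and 14.8 and Table 6, that is, permanent discontinuation due to elevated LFTs. If the earlier visit is intended, keep footnote 2 and amend those places, accepting extra visits in subjects who are not discontinued.
- **Resumption.** Use one criterion throughout, preferably the stricter one in footnote 1 with bilirubin <2×ULN. In Sections 11.7.2.1 and 11.7.2.4 this is a small change to a dosing rule and should be presented as such.

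The cost is a short amendment or clarification letter and, occasionally, a slightly later resumption. There is no statistical cost.

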11.7.3. Cutaneous Events

Subjects participating in Study 205MS303 who develop a mild or moderate cutaneous AE that is not associated with more than 1 systemic symptom or sign do not need to be evaluated by the *Study Dermatologist*; the *Study Neurologist* can complete the Unscheduled Dermatology

CONFIDENTIAL

The information contained herein may not be used, disclosed, or published without the written consent of Biogen MA Inc.

Assessment Visit as soon as possible. In such cases, the *Study Neurologist* should complete the Physician's Global Assessment Scale form. Any subject participating in Study 205MS303 who develops a mild or moderate cutaneous AE that is associated with more than 1 systemic symptom or sign, a severe cutaneous AE (with or without systemic symptoms or signs), or a serious cutaneous AE (with or without systemic symptoms or signs) needs to be evaluated by the *Study Dermatologist* at an Unscheduled Dermatology Assessment Visit as soon as possible. Systemic symptoms associated with a mild or moderate cutaneous AE that would require evaluation by a dermatologist may include, but are not limited to, fever, hematological abnormalities, abnormalities of internal organs (as may be detected by renal and liver function tests), and lymphadenopathy.

[figure not shown]
If the *Study Neurologist* sees the subject prior to the *Study Dermatologist*, the *Study Neurologist* should, if possible, assess the cutaneous AE prior to the subject seeing the *Study Dermatologist*. The information from the assessment by the *Study Neurologist* will be captured in addition to the information from the assessment by the *Study Dermatologist*. If the cutaneous AE is assessed by the *Study Dermatologist* as a mild or moderate cutaneous AE not associated with more than 1 systemic symptom or sign, any follow-up visits can be conducted by the *Study Neurologist*.

A flowchart is presented in [Figure 2](#) to summarize how these subjects will be managed during the study.

CONFIDENTIAL

The information contained herein may not be used, disclosed, or published without the written consent of Biogen MA Inc.

Figure 2: Flowchart for Management of Subjects With Cutaneous AEs

AE = adverse event; PGA = Physician's Global Assessment.

Photographs can be taken by the *Study Neurologist* or designee at these visits for mild or moderate cutaneous AEs that are associated with more than 1 systemic symptom or sign, severe cutaneous AEs (with or without systemic symptoms or signs), or serious cutaneous AEs (with or without systemic symptoms or signs) if they have not been taken by the *Study Dermatologist* (see Section 4.2). The subjects will be asked for their consent to having their dermatological photographs used for educational purposes, if required.

Skin biopsy must be performed in subjects with severe or serious cutaneous AEs (with or without systemic symptoms or signs) at the **Unscheduled Dermatology Assessment Visit**, unless medically contraindicated.

CONFIDENTIAL

The information contained herein may not be used, disclosed, or published without the written consent of Biogen MA Inc.

Skin biopsies from study subjects with severe or serious cutaneous AEs (with or without systemic symptoms or signs) will be sent to a centralized laboratory for evaluation. Results of the skin biopsy will be provided back to the *Study Dermatologist* as soon as possible with a copy sent to the sponsor. Skin biopsy may also be locally evaluated per the discretion of the *Study Dermatologist*.

If the cutaneous AE is suspected to be an allergic or hypersensitivity reaction to study treatment, study treatment must be suspended until consultation with the *Study Dermatologist*. Under the consultation of the *Study Dermatologist*, the subject should also withhold all other non-essential medications, including protocol-required medications (as appropriate), and non-prescription drugs and supplements, at least until the cutaneous event has resolved. The decision to permanently discontinue study treatment should be made by the Investigator in consultation with the *Study Dermatologist*. If an allergic or hypersensitivity reaction to study treatment is confirmed, study treatment must be permanently discontinued.

11.7.4. Gastrointestinal Events of Inflammatory Colitis

For any subject participating in Study 205MS303 who develops symptoms of inflammatory colitis (e.g., persistent diarrhea and abdominal cramps, blood in the stool, and fever), treatment with DAC HYP should be stopped and the subject should be referred to a specialist. Some subjects with mild colitis who require DAC HYP therapy may be able to continue the study treatment if the benefit-risk profile is considered positive per Investigator's assessment and the subject's informed decision.

11.7.5. Lymphadenopathy or Lymphadenitis Events

Any subject participating in Study 205MS303 who develops clinically significant lymphadenopathy or lymphadenitis should be referred to a specialist. Additional diagnostic tests, such as imaging, blood tests, and/or biopsy, should be performed according to the local standard of care.

When diagnostic tests are performed, the results may be requested for internal safety review and, when available, biopsy materials will be sent to a centralized laboratory for evaluation. The results of the central laboratory biopsy report will be provided back to the *Study Neurologist* as soon as possible, with a copy sent to the Sponsor.

Study treatment may continue or be resumed after a temporary suspension in cases of uncomplicated lymphadenopathy if the benefit-risk profile is considered positive per the Investigator's assessment and the subject's informed decision. Subjects who discontinued study treatment for any reason while presenting with ongoing lymphadenopathy or lymphadenitis should be followed until the lymphadenopathy or lymphadenitis has stabilized or resolved or the study has terminated, whichever comes first.

CONFIDENTIAL

The information contained herein may not be used, disclosed, or published without the written consent of Biogen MA Inc.

